5.0 Study Procedures

5.1 Study Design

This study will employ a within-subject experimental design. Each participant will wear, in block randomized order, a standard-of-care prosthetic foot, this same prosthetic foot with a heel-stiffening wedge, this same prosthetic foot but one category stiffer, a dual keel prosthetic foot

intended for load carriage applications, and a powered ankle-foot purported to adapt to changing loads. All study prostheses are commercially available. Each participant, wearing each of the study prostheses, will walk on an instrumented treadmill with no added load and four added load conditions of 13.6 kg: anterior, posterior, intact-side carry, and prosthetic-side carry. The load condition will be presented in block randomized order. The protocol consists of two study visits of no longer than four hours each. A third visit may be needed if data are found to be missing or corrupted, also lasting no longer than four hours.

The anticipated risks of the study include injury to the residual limb (skin irritation or damage) while participating due to wearing the study prostheses (which may be heavier than their as-prescribed prosthesis) or carrying study loads (13.6 kg). Our research prosthetist will discuss any concerns such as low back pain or arthritic joint problems with each participant to determine study suitability and minimize this risk. Some study participants of diabetic/dysvascular etiology may be at risk of injury to the contralateral limb due to carrying study loads. Our research prosthetist will discuss these issues with each participant to establish study suitability. Individual participants in the proposed research are not expected to receive a direct benefit from their participation. The potential benefit of the proposed research is to the veteran lower limb amputee population in general. The anticipated benefit is knowledge of how heel-stiffening wedges, stiffer feet, dual keel prostheses, and powered prosthesis function under varying load conditions. The risks to subjects are low; no life sustaining or life supporting interventions are used as a part of the proposed research protocol. The potential benefit and low risk suggest a favorable risk/benefit ratio.

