5.5 Study Evaluations

Study Prostheses

Each participant will be fit with four different prostheses: (1) a standard-of-care prosthetic foot, (2) this same prosthetic foot with a heel-stiffening wedge, (3) a dual keel prosthetic foot intended for load carriage activities, and (4) a powered ankle-foot purported to adapt to changing loads. For the standard-of-care prosthetic foot, we will use the Sierra prosthetic foot (Freedom Innovations, Irvine, CA). This prosthetic foot is available in sizes 22 to 31 cm (most VAPSHCS prescriptions are from size 27 to 29 cm), stiffness categories 1 to 9 (most VAPSHCS prescriptions are categories 5, 6, or 7). For adjustment of heel stiffness and roll-over characteristics, the Sierra prosthetic foot comes standard with an optional heel wedge that, when affixed to the heel keel as directed, results in a one category increase in stiffness of the heel keel. We also will use the only commercially available dual keel foot, the Thrive (Freedom Innovations, Irvine, CA). This prosthetic foot is available in sizes 22 to 31 cm and stiffness categories 1 to 9 (note: the stiffness categories of the Sierra and Thrive prosthetic feet are identical). For the powered ankle-foot, we will use the only commercially available powered ankle-foot, the Empower (Otto Bock, Austin, TX). This prosthetic ankle-foot is available with a foot keel in sizes 25 to 30 cm and three body-weight dependent stiffness categories.

Load Carriage

To add anterior and posterior loads, subjects will don a weighted and padded pack fitted with additional straps to secure it to the torso (Classic; Camelbak, Petaluma, CA). The pack will have weights placed inside it so that the total mass is 13.6 kg. To allow the participant to carry the load on the intact- and prosthetic-sides of their torso with their arms, the straps from the padded backpack will be removed or constrained.

Experimental Protocol

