After at least one overnight rest period, we will ask the subjects to return to the laboratory for the second study visit. Subjects will be asked to don body fitting garments, after which sixty-two 14 mm reflective markers will be placed on each subject in locations consistent with a modified version of Vicon's Plug-in-Gait full-body model (Centennial, CO). Anthropometric measures will be recorded for static and dynamic modeling. The Plug-In Gait model will be modified by adding reflective markers at the medial malleolus, medial elbow, and first and fifth metatarsal heads of the feet. The thigh and upper arm segments will be tracked with marker clusters instead of wands. The shank segments will be tracked with markers placed on the fibular head and tibial tuberosity instead of tibial wands. Hip joint centers will be calculated using regression equations based on the inter-ASIS distance of the pelvis.

To help understand how individuals achieve biomechanical performance deviations, we will collect surface EMG data from the primary muscle groups involved in human walking. Specifically, we will shave the skin of the tibialis anterior (TA), medial gastrocnemius (GAS), soleus (SOL), vastus medialis (VAS), rectus femoris (RF), biceps femoris long head (HAM), gluteus medius (GMED), and gluteus maximus (GMAX) of the intact leg along the muscle line of action between the origin and insertion points, and clean it with alcohol to decrease impedance. For the residual limb, we will do the same for the VAS, RF, HAM, GMED, and GMAX. Disposable dual surface EMG electrodes with 2.0-cm spacing will then be applied and connected with a pinch-style terminal to a sensor probe (Noraxon, Inc.) with reference electrode and preamplifier. Each electrode will be held securely in place with Coban (3M, Inc.). Data from the probes will be wirelessly transmitted to a receiver where the data will be processed, synced, and stored in real-time with our existing motion capture system (Vicon, Centennial, CO).

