Using the same methods as the first study visit, subjects will be blinded to and fit with each study prosthetic foot in random order. After the first study prosthesis is fit, subjects will walk on our existing instrumented treadmill (AMTI, Watertown, MA) their SSWS determined during the first study visit. In random order, subjects will be asked to walk for one minute with no load and the four added load conditions. Kinematic and kinetic biomechanical data will be collected during each one-minute trial using a 12-camera Vicon system (Vicon, Centennial, CO) and two force plates embedded in the split-belt treadmill. Rest breaks will be provided as needed. After each load condition, we will ask the subject to rate their satisfaction with the functional performance of the study prosthesis using an 11-point Likert scale (0-10) where 0 is defined as completely dissatisfied and 10 as completely satisfied. Subject participation in the study will conclude after they have worn all four study prostheses.

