The satisfaction data from the experiment will be aggregated using project specific software (Matlab; Mathworks, Natick, MA). We hypothesize that there exists a study prosthesis that maximizes satisfaction across the different load conditions. The statistical analyses to test this secondary hypothesis will require a two-factor (prosthesis, load condition) Friedman analysis of variance (ANOVA). This analysis will test for differences between the four different study prostheses across the four different load conditions. The experiment-wise significance will be set a priori at an alpha level of $p<0.05$ and a Bonferroni adjustment will be applied for multiple comparisons. All statistical analyses will be performed using existing VA enterprise software (SPSS Statistics v22; IBM, Inc.). Exact p-values will be reported for each test.

Surface EMG data from the walking trials will be processed with existing custom algorithms in Matlab (Mathworks, Inc.). The collected data will be high-pass filtered (bidirectional Butterworth, 4th order, 50 Hz cutoff frequency), demeaned, and rectified, and then further smoothed using a Version 2.5; 5/14/2021 VA Puget Sound IRB Protocol Template – Version: 12/2015 Page **15** of **20**

moving root-mean-square (RMS) window of 80-ms. Subject average RMS profiles for each muscle at each condition will be normalized to the average peak RMS value of the same muscle for each stiffness setting while walking on the 0° condition. The kinematic and kinetic data will be filtered with a 4th-order Butterworth filter with cut-off frequencies of 6 Hz and 20 Hz, respectively, using Visual3D (C-Motion, Inc.). This data will be used to support the biomechanical observations.

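### The EMG normalisation rule refers to a walking condition this trial does not have; read as each foot's own no-load peak, it would remove proportional foot effects on amplitude common to all loads

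*Protocol*

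**What the plan says.** Protocol 5.6, Secondary Analyses, describes the EMG processing (filtering, rectification, moving RMS). It then says that each subject's average profile, for each muscle and condition, is scaled to that muscle's average RMS peak "for each stiffness setting while walking on the 0° condition".

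The walking trials themselves are set out in Protocol 5.5, Experimental Protocol: "In random order, subjects will be asked to walk for one minute with no load and the four added load conditions". This is repeated for each study foot on an instrumented treadmill at the participant's self-selected speed.

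The purpose of the EMG is also given in 5.5: "To help understand how individuals achieve biomechanical performance deviations, we will collect surface EMG data". Section 5.6 adds that the data are there to back up the biomechanical findings. None of H1 to H5 in Protocol 3.0 concerns EMG, 5.6 plans no EMG test, and the SAP does not list EMG among its outcomes.

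**The concern.** The denominator is defined by two terms, a 0° walking condition and a stiffness setting, that do not name levels of this trial's factors. Whoever processes the data must therefore substitute something, and the protocol does not say what.

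The choice matters. The wording asks for a separate reference for each setting, so the most natural substitute is each foot's own no-load trial. That gives every foot a different denominator. Yet the comparison that the EMG should help explain is between feet within each load (Protocol 5.6), and Protocol 3.0 counts no added load as one of those conditions. A foot-specific denominator takes out part of the between-foot difference before anyone looks at it. A descriptive EMG summary could then suggest that muscles work equally hard on all feet when they do not.

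**Working it through.** The protocol gives no EMG figure to reproduce. The check has two parts: whether the reference exists, and what the likely substitutes do to the foot contrast.

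**1. Does the reference exist?**

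- Load: Protocol 5.1 has participants walk "with no added load and four added load conditions of 13.6 kg: anterior, posterior, intact-side carry, and prosthetic-side carry". That is five load levels and no slope.
- Angle: the only other figure in degrees is the 6.8° heel wedge in the Fig. 2 caption of Protocol 2.0. It is a foot component, not a walking surface.
- Stiffness: elsewhere in the protocol this is a product category. The foot list in 5.1 includes "this same prosthetic foot but one category stiffer, a dual keel prosthetic foot", and 5.5 says the wedge raises heel-keel stiffness by one category. The term could therefore separate the standard, wedged and stiffer feet. It does not describe what sets the dual keel or powered foot apart.
- Section 5.5 also says "Each participant will be fit with four different prostheses" and leaves out the stiffer foot. On that list only the wedged foot differs from the standard foot by stiffness alone.

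**2. Algebra.** Write peak EMG for foot f and load l as E(f,l) = m × F_f × L_l × I_fl, where m is the participant and muscle level, F the foot effect, L the load effect and I the foot-by-load interaction, with I = 1 at no load.

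- Own-foot no-load reference: E(f,l)/E(f,0) = (L_l/L_0) × I_fl. F_f drops out.
- One foot's no-load trial as common reference (foot s): E(f,l)/E(s,0) = (F_f/F_s) × (L_l/L_0) × I_fl. F_f stays.
- Mean no-load peak over feet: also a single denominator per participant and muscle, so F_f stays.

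For a foot that raises the peak by 20% at every load, the own-foot ratio is 1.20/1.20 = 1.00. For 20% unloaded and 30% loaded it is 1.30/1.20 = 1.083, so 8% is shown instead of 30%.

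**3. Illustration with assumed peaks.** The load effect for posterior carry is set at 1.20. The last three columns add an assumed interaction under load: dual keel −10%, powered +10%.

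| Foot | No load, raw | Posterior, raw | Own-foot ref. | With interaction, raw | Own-foot ref. | Ref. = standard foot, no load |
|---|---|---|---|---|---|---|
| Standard | 100 | 120 | 120% | 120 | 120% | 120% |
| Wedge | 95 | 114 | 120% | 114 | 120% | 114% |
| Stiffer | 90 | 108 | 120% | 108 | 120% | 108% |
| Dual keel | 110 | 132 | 120% | 118.8 | 108% | 118.8% |
| Powered | 80 | 96 | 120% | 105.6 | 132% | 105.6% |

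Without interaction, all five feet become identical. With interaction, the load response survives (118.8/110 = 1.08; 105.6/80 = 1.32), but the powered foot goes from the lowest raw value to the highest normalised one. The mean no-load peak over feet is (100 + 95 + 90 + 110 + 80)/5 = 95. Dividing by 95 rescales every entry equally and changes no ratio between feet.

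**4. Simulation.** Assumed inputs, not from the documents: 20 participants, two feet, log-scale SD 0.15 per foot-and-load cell, paired t-test at two-sided 0.05, 4,000 runs.

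| True effect under load | Common reference | Own-foot reference |
|---|---|---|
| Foot 20% lower at all loads | detected in 99.5% | 5.2%, about the nominal error rate |
| Foot 20% lower only under load | 99.3% | 87.9% |

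The second row is lower with the own-foot reference because the contrast then uses four noisy cells instead of two: SD 0.15 × √4 = 0.30 against 0.15 × √2 = 0.21 on the log scale.

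**The case against.** A reader might infer that the rule wipes out every foot difference in the EMG. The documents do not support that, for these reasons:

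- Only proportional effects common to all loads cancel. Foot-by-load differences and profile shape survive. They are of direct interest here: Protocol 2.0 describes a dual keel that stiffens as load is added, and 5.1 a powered foot said to adapt to load.
- A common additive effect is distorted, not erased. With illustrative peaks of 100 unloaded and 150 loaded, and a second foot 20 higher at both, the ratios are 150/100 = 1.50 and 170/120 = 1.42. The foot with more activity then looks lower.
- The no-load values need not be exactly 100% for every foot. The denominator is an average peak and the numerator an average profile. If peaks are taken stride by stride, the two can differ slightly. The comparison of peak amplitude is still essentially lost.
- It would be too strong to say that stiffness plays no part in the design, since the stiffer and wedged feet are a partial counterpart.
- The harm depends on a substitute reading. The documents do not show which denominator will be used, and a no-load reference averaged over feet would cancel nothing.

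All of this stands and limits the point. It does not rescue the sentence: nothing in the protocol or SAP defines the 0° condition, and whether foot differences in amplitude show up depends on a choice left unstated.

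**Conclusion.** Wrong as written. That the named reference condition is missing from this trial follows from the text alone and needs no assumption. The loss of foot effects is conditional: it holds if the analyst uses each foot's own no-load peak and to the extent that foot effects are proportional. Under those conditions a load-independent foot effect is removed in full, whatever its size, and rankings within a load can change. The table and simulation show the mechanism under assumed inputs; they are not estimates for this trial.

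A reader might also infer that the trial's main conclusions are at risk. They are not. The EMG has no hypothesis, power calculation or test, and no primary outcome or SAP analysis uses it. The consequence is confined to the supportive account of how participants adapt to each foot.

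**What to change.** Replace the normalisation sentence in Protocol 5.6 with one that:

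- names one reference per participant and muscle, applied to all feet and all loads recorded in the same session (the same electrode placement), for example the average peak RMS in the no-load trial on the standard-of-care foot;
- gives a fallback if that trial is missing: the mean no-load peak over all feet with usable data;
- says that data from a third visit are divided by a reference trial collected at that visit, on the assumption that electrodes will have been reapplied;
- drops the 0° and stiffness-setting wording.

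Any EMG report should state which denominator was used.

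The cost is one sentence and one changed denominator in the processing code. Visit 2 already includes the no-load trials. A third visit may need one extra one-minute reference trial. The downside is that a single reference trial is more exposed to loss or noise, which the averaged fallback addresses. The standard-of-care foot is one workable choice; any reference common to all feet would serve.

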5.7 Withdrawal of Subjects

This is not a treatment study; withdrawing or being terminated from this study will not have an impact on participant safety. A study clinician or the PI may withdraw a participant without their consent if he or she feels that it is not in a participant's best interest to continue in the study or the person is unable to complete the study procedures. All data previously collected from participants who withdraw or are withdrawn will be kept and may be used in the study data analysis. Participants may withdraw at any time by informing the Research Coordinator and/or the PI. If a participant wants to withdraw or we choose to withdraw a participant, while she/he are using a study prosthesis, we will arrange for their as-prescribed prosthesis to be returned and fit to the participant.

6.0 Reporting

All safety information on AEs, SAEs, unanticipated events or problems, and protocol deviations will be collected. This information will be collected at study visits and whenever subjects call to report a problem. The information will be collected on VA IRB forms (Report of a SAE and/or Problem Form, or Report of Problems (ROP) Form) and in AE log forms as needed. Safety data will be collected on an as-needed basis and will begin upon enrollment into the study. All safety reporting requirements will be followed. Any anticipated AEs will be recorded on a log sheet and reported annually with the CRQ.

If we become aware of relevant findings or information that may affect subjects' health or welfare, we will contact subjects by phone and/or a letter to notify them.

7.0 Privacy and Confidentiality

This study will not use or disclose Protected Health Information (PHI). No Certificate of Confidentiality will be required. It is possible, although unlikely given the impersonal nature of the data collected, that participants may experience a loss or invasion of privacy or confidentiality because of participation in this study. The risk of harm is minimal and the protections described here will be followed.

De-identified, non-sensitive electronic data labeled with the study assigned codes, and all 18 HIPAA identifiers removed or converted to de-identified format, may be stored on password-protected equipment but will not be encrypted. De-identified data files may be sent off-site via email, file transfer software, and/or other electronic media to our biostatistician, off-site collaborators, and between study investigators.

Any consented photography or video will protect participants' identity (e.g., by obscuring the subject's face and any identifying marks like tattoos). The videos and photos may include the participant's entire body, but they will be anonymized during data processing; the participant's

face will be blurred, any identifying marks will be covered or blurred, and then the original file will be deleted. If a participant's voice is accidentally recorded, that section of video would be altered prior to any use outside of the VA study team. The video camera and the recording media will be stored in a locked office at the VAPSHCS. Photos and videos that do not contain identifiable information may also be stored on password-protected computers for future use in scientific presentations and publications. Study records with PHI/PII will be stored until the end of the study, and for a minimum of 6 years after the study is completed (in accordance with the records retention schedule); they will be destroyed using VA approved procedures. Hard copy data with identifiable and/or sensitive information will be shredded per VA approved policies. Electronic data containing identifiable information will be wiped using VA approved software. De-identified data will be stored indefinitely.

VA medical records will be created, or updated, for each participant. The medical record will include information about enrollment in this study, cholesterol test results (if done at VA), and information about any other medical treatment received (if needed) that is related to this study. All authorized users of the national VA medical records system can have access to the medical record. This may include health insurance companies who are being billed for medical costs. This record will be kept forever.

8.0 Communication Plan

This is not a multi-site study. If students or staff at the University of Washington are participating as study staff at the VA, the PI will assure that the appropriate approval is obtained from the UW Human Subjects Division.

9.0 Information Security and Data Storage/Movement

Electronic data with PHI/sensitive information will be stored on the secure server at the VAPSHCS. These data will only be accessed by authorized study personnel. Hardcopies of VA sensitive data and documents with PHI will be stored in a locked file cabinet in a locked office at the VAPSHCS. Study files/data with PHI or sensitive information will not be sent off-site. This is a locked facility to which only study investigators have access. Identifiable data will not be transmitted, transported, or stored on portable media or laptops outside of the VA, and the data will only be accessed by authorized VA study staff. We will notify the Information Security Officer (ISO) of the location of the hardcopy data/files via the Data Inventory form. If study data is improperly used or disclosed, we will notify the ISO and Privacy Officer within one hour of becoming aware of the issue.

Study staff will only have access to the minimum necessary identifiable information needed to perform their role. Study staff that depart the VA or are removed from the research team will be promptly removed from the research application and will no longer have access to sensitive study data.

Study data will be labeled with a study assigned code and de-identified data sets will be created/used when data is made publicly available and transmitted without restriction. A copy of de-identified data will also be made available to public search, retrieval, and analysis per the limitations the Data Management Access Plan (DMAP). The key to the code will be stored separately from the study data, and only designated VA study staff will have access to it.

De-identified, non-sensitive electronic data labeled with the study assigned codes, and all 18 HIPAA identifiers removed or converted to de-identified format, may be stored on password-protected equipment (computers/laptops/SD cards) but will not be encrypted. De-identified data files may be sent off-site via email, file transfer software, and/or other electronic media to our biostatistician ([name], MS), off-site collaborator ([name]), and between study investigators. Off-site collaborators will only have access to de-identified data.

Study records with PHI/PII will be destroyed using VA approved procedures and in accordance with the records retention schedule after the study is completed. Hard copy data with identifiable and/or sensitive information will be shredded per VA approved policies. Electronic data containing identifiable information will be wiped using VA approved software. De-identified data will be stored indefinitely.

